**15.3.8 Efficacy Analyses**

To assess treatment effect, change from baseline in weekly systolic and diastolic blood pressure values will be analyzed using a mixed effect model that includes fixed effects of strata, treatmentvisit, and visit-by-treatment interaction, and a random effect of subjects. Estimates of the adjusted least-squares (LS) mean, difference in LS means, and corresponding 95% CIs will be obtained from the model. The same methodology will be used for assessments obtained using ambulatory blood pressure monitors. The influence of baseline factors, such as race, may be included in the models if sufficient data is available for secondary analyses. In addition, the average change of both systolic and diastolic blood pressure from baseline will be compared between treatment groups using analysis of covariance. Additional details on the efficacy analysis will be described in the statistical analysis plan.

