3. GENERAL STATISTICAL METHODS

3.1. Sample Size Justification

A total sample size of 116 randomized subjects, divided into 2 arms (placebo or B244) of 58 subjects each allows for a dropout rate of 10%. It is expected that each strata will have at least 52 subjects with sufficient data needed determine the effect of the IP on blood pressure.

With the planned number 52 subjects per arm, the study is powered 80%, to detect a treatment effect = 5.8 (mean change in systolic blood pressure from baseline), standard deviation (SD) = 10.5 (higher SD than was observed in Phase 1b/2a), with alpha = 0.05, using a 2-sample t-test.

Based on the above sample size, the study is powered 90% to detect the treatment effect of 5.8 (mean change in systolic blood pressure from baseline) and SD = 9, using a 2-sample t-test, that was observed in the Phase 1b/2a study.

In the planned analyses, mixed models will be used to account for the correlation of the assessments over time and provide a more robust analysis of the endpoint.

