Tabulations will be produced for appropriate demographic, baseline, efficacy, and safety parameters. For categorical variables, summary tabulations of the number and percentage of subjects within each category (with a category for missing data) of the parameter will be presented. For continuous variables, the number of subjects, mean, median, SD, minimum, and maximum values will be presented.

Formal statistical hypothesis testing will be performed on the primary and secondary efficacy endpoints with all tests conducted at the 2-sided, 0.05 level of significance. Comparisons of baseline characteristics will be performed in order to assess comparability of the treatment arms. Summary statistics will be presented, as well as 2-sided 95% CIs on selected parameters, as described in the sections below. P-values will be rounded to 4 decimal places. P-values that round to 0.0000 will be presented as <0.0001 and p-values that round to 1.00 will be presented as >0.9999.

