4.3.1. Weekly In-Clinic Blood Pressure

To assess treatment effect, change from baseline in weekly systolic and diastolic blood pressure values will be analyzed using a mixed effect model that includes the change from baseline at Days 7, 14, 21, and 28. Day 42 will not be used in the primary endpoint analysis. The model will include stratification factors of spray number and hypertension and baseline blood pressure as covariates, with treatment group (B244 or placebo) and visit as fixed effects, and subject as a random effect. The model will include the following interaction terms: treatment*visit, strata*visit, treatment*strata, and treatment*strata*visit. Estimates of the adjusted LS mean, difference in LS means, and corresponding 95% CIs will be obtained from the model.

Linear contrasts of the differences between each treatment group (4 doses or 8 doses) and placebo at each visit will be used to compare the results between treatments using LS means between each active treatment group and placebo. Nominal 2-sided p-values and 95% CIs will be reported at Days 7, 14, 21, and 28.

Treatment group comparisons within each strata will be an exploratory analysis.

Mixed models will be implemented using PROC Mixed in SAS, using an unstructured within-subject covariance matrix and denominator degrees of freedom from the Kenward-Roger method. Other covariance matrices (first order autoregressive process [AR(1)], compound symmetry, independent) may be utilized in the event that the unstructured matrix does not converge. In this event, the matrix structure that converges provides the lowest akaike information criterion (AIC) value will be selected.

This modeling will be performed for both systolic and diastolic blood pressure, in both the ITT and PP populations.

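### The primary mixed model has one covariance parameter too many, and every structure in its fallback list assumes equal variance at all visits, so Day 28 standard errors could be misstated if the fallback is used

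*SAP*

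**What the plan says.** SAP 4.3.1 models change from baseline at Days 7, 14, 21 and 28, with "treatment group (B244 or placebo) and visit as fixed effects, and subject as a random effect". The same section says the model is run in PROC MIXED "using an unstructured within-subject covariance matrix and denominator degrees of freedom from the Kenward-Roger method".

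The fallback reads: "Other covariance matrices (first order autoregressive process [AR(1)], compound symmetry, independent) may be utilized in the event that the unstructured matrix does not converge". Among the structures that converge, the one with the lowest AIC is taken. Nominal p-values and 95% confidence intervals are reported at each of the four visits. SAP 3.2 has "all tests conducted at the 2-sided, 0.05 level of significance".

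Two other places describe the model. Protocol 15.3.8 lists strata, treatment, visit, "and visit-by-treatment interaction, and a random effect of subjects", and names no covariance structure. The note under Table 14.2.1A in the SAP lists baseline blood pressure, treatment, visit, treatment-by-visit and hypertension status, and no random subject effect.

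**The concern.** An unstructured matrix for four visits already contains every variance and covariance among them. A random subject effect adds a constant to all of those elements, so it carries no new information and cannot be separated from the matrix. A programmer following SAP 4.3.1 would fit a redundant model, and one following the table note would not.

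The redundancy matters because of what may follow. It can leave a singular Hessian or stop the fit from converging. The SAP acts only on non-convergence, does not define it, and leaves the use of another structure optional. The structures then on offer all fix one variance for every visit, while inference is reported visit by visit. If variability changes over the four weeks, the Day 28 test and interval would be too liberal or too conservative. SAP 4.3.1 also fits the model separately in pre-hypertensive and Stage 1 subjects, where smaller numbers give an unstructured fit less support.

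**Working it through.** **1. The plan's own figures.** From SAP 3.1: 52 per arm, effect 5.8 mmHg, "with alpha = 0.05, using a 2-sample t-test". The standard error of the difference is SD × √(2/52) = SD × 0.1961, and approximate power is Φ(5.8/SE − 1.96).
- SD 10.5: SE = 2.059 and power = Φ(2.817 − 1.96) = 80.4% (79.7% with the noncentral t).
- SD 9: SE = 1.765 and power = Φ(3.286 − 1.96) = 90.8% (90.2% with the noncentral t).

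Both stated powers (80% and 90%) reproduce. They rest on a t-test and do not involve the covariance model.

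**2. Parameter count.** Write the covariance of the four visits as V = s²·J + R, where s² is the random subject variance, J is a 4×4 matrix of ones and R is the within-subject matrix. V has 4×5/2 = 10 distinct elements. The rank of the derivatives of V with respect to the parameters is:

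| R, with a random subject effect | Parameters | Rank |
|---|---|---|
| Unstructured | 11 | 10 |
| Compound symmetry | 3 | 2 |
| AR(1) | 3 | 3 |
| Independent | 2 | 2 |

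The primary specification is therefore over-parameterised by one, and so is compound symmetry if the random effect is kept in the fallback.

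**3. Effect of the redundancy alone.** In one simulated dataset, moving s² from 0 to 25 while holding V fixed left −2 log L at 1923.53 and the Day 28 SE at 2.075. Only the split between s² and R is undetermined. V is identified.

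**4. Effect of an equal-variance fallback.** With or without the random effect, all three listed structures give every visit the same total variance. With complete data the Day 28 contrast is a difference in visit means. Its reported SE then uses approximately the pooled SD, √(mean of SD_t²), instead of SD_28. The ratio of reported to true SE is k = SD_pooled/SD_28, from which the sample size cancels. Two-sided type I error is 2[1 − Φ(1.96k)].

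Example, SDs 9/9.5/10/10.5: the mean variance is (81 + 90.25 + 100 + 110.25)/4 = 95.375, so SD_pooled = 9.77 and k = 9.77/10.5 = 0.930. Then 1.96 × 0.930 = 1.823 and the error is 6.8%.

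The documents give no SD by visit, so every row below is an assumption.

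| Assumed SD at Days 7/14/21/28 | Pooled SD | k | Reported SE (true SE) | Day 28 type I error |
|---|---|---|---|---|
| 10.5 at all visits | 10.50 | 1.000 | 2.059 (2.059) | 5.0% |
| 9/9.5/10/10.5 | 9.77 | 0.930 | 1.915 (2.059) | 6.8% |
| 8/8.8/9.7/10.5 | 9.30 | 0.885 | 1.823 (2.059) | 8.3% |
| 8/9/10/11 | 9.57 | 0.870 | 1.876 (2.157) | 8.8% |
| 12/11.5/11/10.5 | 11.26 | 1.073 | 2.209 (2.059) | 3.6% |

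**5. Whether the AIC choice helps.** The choice among the three structures, fitted without a random effect, was simulated with 1,500 replicates per scenario, 52 per arm, complete data and no covariates. The true correlation was either constant at 0.5 or AR(1) at 0.7. Day 28 type I error was 5.4–5.6% with equal SDs, 6.1–6.3% for 9 to 10.5, and 8.5–9.3% for 8 to 10.5. An unstructured fit to the same data gave 5.4–5.5%, 4.3–4.7% and 5.6–6.2%. Monte Carlo SE was about 0.6–0.8 points. AIC found the right correlation shape almost every time and never chose independent, but it had no structure with unequal variances to choose.

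**The case against.** The strongest reply is that a standard MMRM was intended. SAP 3.2 and 3.10 use that name, SAP 3.10 speaks of estimating the covariance between time points, and the table note has no random effect. The random-effect phrase may be loose wording for within-subject correlation. This is plausible, and it limits the severity. It does not settle the text: the same note names an outcome that does not belong to this trial (NIS-W), so it is weak evidence against SAP 4.3.1.

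Four stronger readings are tempting, and the documents do not support them.
- **That the model cannot be fitted, or that the redundancy makes the Day 28 SE wrong.** V is identified. Because the random-effect derivative lies within the span of the unstructured ones, the Kenward-Roger result with any generalised inverse equals that of the unstructured model alone. How PROC MIXED would behave is not in the documents.
- **That the fallback is the likely outcome.** It is conditional and optional, and no probability of non-convergence can be derived for four visits and about 104 subjects.
- **That the error rate is not 5%.** This is so only if the fallback is used and variances differ by visit. The direction is also open: falling variance makes the test conservative.
- **That an independent structure without a random effect would inflate the error severely.** That concerns a contrast averaged over visits, whereas SAP 4.3.1 reports contrasts at each visit, and AIC would normally reject the structure.

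It also stands that the supportive Day 28 ANCOVA in SAP 4.3.1.1 uses Day 28 data only, so neither problem touches it. It is a check on the primary result and does not correct the primary specification.

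**Conclusion.** The concern holds as a should-fix. Two parts need no assumed data: the model in SAP 4.3.1 has 11 covariance parameters of which 10 are identifiable, and it disagrees with the Table 14.2.1A note. The third part is conditional. If the fallback is used and SDs differ by visit, Day 28 type I error would run from about 3.6% to 8.8% over the patterns tabulated. With equal SDs it is 5%. These figures assume complete data, a normal approximation and the listed SDs. Sample size and power are unaffected.

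**What to change.** Amend SAP 4.3.1 as follows.
- Delete the random subject effect. Fit REPEATED visit / SUBJECT=subject TYPE=UN with Kenward-Roger degrees of freedom.
- Make SAP 4.3.1 and the Table 14.2.1A note state the same model. Because Protocol 15.3.8 names a random effect of subjects, record the change in SAP section 5.
- Define non-convergence to include a Hessian that is not positive definite.
- Replace the AIC choice by a fixed order that starts with heterogeneous-variance structures, for example TOEPH, then ARH(1), then CSH. Other heterogeneous orders would also serve. Keep a homogeneous structure only as a last resort, with a robust standard error and a named degrees-of-freedom method. Drop the independent structure.

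The cost is SAP wording, with no new data and no change to sample size. The downside is a few more covariance parameters to estimate if the fallback is needed.

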	Mean (SD)	xx.x (xx.xx)	xx.x (xx.xx)	xx.x (xx.xx)	xx.x (xx.xx)	xx.x (xx.xx)
	Median	xx.x	xx.x	xx.x	xx.x	xx.x
	Min, Max	xx, xx	xx, xx	xx, xx	xx, xx	xx, xx
Percent Compliance [3]	n	xx	xx	xx	xx	xx
	Mean (SD)	xx.x (xx.xx)	xx.x (xx.xx)	xx.x (xx.xx)	xx.x (xx.xx)	xx.x (xx.xx)
	Median	xx.x	xx.x	xx.x	xx.x	xx.x
	Min, Max	xx, xx	xx, xx	xx, xx	xx, xx	xx, xx

[1] Cumulative study drug exposure = weight of the 3 drug bottles at last visit - weight of the 4 drug bottles at first dispense.

[2] Amount of product used per day = change / number of days the subject was on treatment.

[3] Percent compliance = (Net weight of study drug) / (Expected net weight for 28 days of use) × 100.

Source: [Listing 16.2.5.1](#), [Listing 16.2.5.2](#)

PROGRAM NAME: XXXXXXXXXXXXXXXXXXXXXXXXXXXXXXXXXXXXXXX

DATE: HH:MM/DDMMYYYY

Repeat for:

Table 14.1.4.1B Summary of Drug Exposure (PP Population)

Table 14.2.1A

Summary of Values and Change from Baseline for Systolic and Diastolic Blood Pressure - Mixed Model Analysis (ITT Population)

Parameter: Systolic Blood Pressure

Visit	Actual/ Change	Statistic	B244			
			4 Sprays (N=xx)	8 Sprays (N=xx)	All B244 (N=xx)	Placebo (N=xx)
Baseline	Actual	n	xx	xx	xx	xx
		Mean (SD)	xx.x (xx.xx)	xx.x (xx.xx)	xx.x (xx.xx)	xx.x (xx.xx)
		Median	xx.x	xx.x	xx.x	xx.x
		Min, Max	xx, xx	xx, xx	xx, xx	xx, xx
Day 7	Actual	n	xx	xx	xx	xx
		Mean (SD)	xx.x (xx.xx)	xx.x (xx.xx)	xx.x (xx.xx)	xx.x (xx.xx)
		Median	xx.x	xx.x	xx.x	xx.x
		Min, Max	xx, xx	xx, xx	xx, xx	xx, xx
	Change	n	xx	xx	xx	xx
		Mean (SD)	xx.x (xx.xx)	xx.x (xx.xx)	xx.x (xx.xx)	xx.x (xx.xx)
		Median	xx.x	xx.x	xx.x	xx.x
		Min, Max	xx, xx	xx, xx	xx, xx	xx, xx
		LS MEAN (SEM)	xx.x (xx.xx)	xx.x (xx.xx)	xx.x (xx.xx)	xx.x (xx.xx)
		95% CI	xx, xx	xx, xx	xx, xx	xx, xx
		LS MEAN Difference B244 - Placebo (SEM)	xx.x (xx.xx)	xx.x (xx.xx)	xx.x (xx.xx)	xx.x (xx.xx)
		95% CI	xx, xx	xx, xx	xx, xx	xx, xx
		P-value [1] (vs Placebo)	0.xx	0.xx	0.xx	0.xx
		P-value [1] (vs 8 Sprays)	0.xx			
Day 14		<as above in Day 7>				
Day 21		<as above>				
Day 28		<as above>				
Day 42		<repeat Actual and Change parameters only>				

Note: Day 42 is not included in model. In the mixed-effect model repeated measures (MMRM) model, the outcome variable is change from baseline in NIS-W. The model includes baseline blood pressure as covariate and fixed effect terms including treatment group, visit, treatment-by-visit interaction and hypertension status.

[1] P-value is derived from the contrast testing at each visit using the MMRM model.

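### The SAP powers pooled B244 versus placebo, but never names that contrast or its time point as the primary test, and it specifies the mixed model inconsistently

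*SAP*

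**What the plan says.** **Sizing.** SAP 3.1 divides 116 randomized subjects into placebo and B244, 58 each, and expects 52 evaluable per arm. It claims 80% power for a 5.8 mmHg effect at SD 10.5 and 90% at SD 9, with a two-sample t-test. Protocol 15.1 describes the same two groups of 58 as the 4-pump and 8-pump cohorts. SAP 5 records the change of SD from 11 to 10.5 but not the change in what the groups are.

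**Endpoint and method.** SAP 4.3 gives the primary endpoint as the fall in in-clinic systolic pressure from Day 1A through Day 28. SAP 3.10 says the primary analysis uses MMRM. SAP 3.2 sets two-sided 0.05 for every formal test, and SAP 3.7 declines adjustment for multiple endpoints without mentioning doses or visits.

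**Contrasts.** SAP 4.3.1 states: "Linear contrasts of the differences between each treatment group (4 doses or 8 doses) and placebo at each visit will be used", and then "Nominal 2-sided p-values and 95% CIs will be reported at Days 7, 14, 21, and 28". The Table 14.2.1A shell has columns for 4 sprays, 8 sprays, All B244 and one placebo group, with p-values against placebo at each of the four visits. Its note reads "P-value is derived from the contrast testing at each visit using the MMRM model". None is marked primary.

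**Model.** On strata and baseline, SAP 4.3.1 says: "The model will include stratification factors of spray number and hypertension and baseline blood pressure as covariates". Treatment has two levels there: "with treatment group (B244 or placebo) and visit as fixed effects". On interactions it says: "The model will include the following interaction terms: treatment*visit, strata*visit, treatment*strata, and treatment*strata*visit". It adds: "Treatment group comparisons within each strata will be an exploratory analysis". The Table 14.2.1A footnote lists a baseline covariate and "fixed effect terms including treatment group, visit, treatment-by-visit interaction and hypertension status", and names the outcome as NIS-W, which is not a variable of this trial. Protocol 15.3.8 lists strata, treatment, visit and visit-by-treatment, with no treatment-by-strata term and no baseline covariate.

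**The concern.** A power statement belongs to one test. Here the test with the stated power is not designated, and the contrasts written out in the efficacy section are different ones with about half as many active subjects. Someone following SAP 4.3.1 literally would report two dose-specific results at each of four visits. Someone following the shell would have a third, pooled result at each visit.

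The time point is also open. A decrease through Day 28 can mean the change at Day 28, which the supportive ANCOVA in SAP 4.3.1.1 favours. It can also mean an average over the treatment visits: Protocol 14 works with average values, and Protocol 15.3.8 compares an average change between groups.

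If the deciding contrast can be chosen after the results are seen, the 5% error rate is not kept. If the model can be chosen as well, the same data can give more than one pooled estimate.

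**Working it through.** **Inputs.** From SAP 3.1: effect 5.8 mmHg, SD 10.5 or 9, 52 evaluable per arm. From SAP 3.2: two-sided 0.05. SAP 1.2.2 allocates equally to four groups (two treatments by two spray numbers), so 104 / 4 = 26 evaluable per group. SAP 3.5 and the shells pool placebo: 26 + 26 = 52.

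**Power.** SE = SD × √(1/n1 + 1/n2). Power comes from the noncentral t with noncentrality 5.8 / SE and n1 + n2 − 2 degrees of freedom.

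| Comparison | n | SE (SD 10.5 / 9) | 5.8 / SE | Power (SD 10.5 / 9) |
|---|---|---|---|---|
| Pooled B244 v placebo | 52 v 52 | 2.059 / 1.765 | 2.82 / 3.29 | 79.7% / 90.2% |
| One dose v pooled placebo | 26 v 52 | 2.522 / 2.162 | 2.30 / 2.68 | 62.2% / 75.5% |

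The first row reproduces SAP 3.1. The second row is the power of each contrast written out in SAP 4.3.1. Its effect detectable with 80% power is 7.2 mmHg (SD 10.5) or 6.1 mmHg (SD 9). To give one dose 80% power for 5.8 mmHg at SD 10.5 would take about 40 + 40 + 80 = 160 evaluable subjects, against 104 planned.

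**False-positive chance at Day 28.** Write a, b and p for the 4-spray, 8-spray and pooled placebo means, in units of σ²/52. Then Var(a − p) = 2 + 1 = 3, Var((a + b)/2 − p) = 1 + 1 = 2, Cov(a − p, b − p) = 1 and Cov(a − p, (a + b)/2 − p) = 1 + 1 = 2. The two dose contrasts therefore correlate at 1/3, and each correlates with the pooled contrast at 2/√6 = 0.82. Simulation of null trials with these group sizes gives:

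- any of the three at p < 0.05: about 10.4% two-sided, and about 5.2% counting only results that favour B244;
- the pooled contrast alone: 5.0% and 2.5%.

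No between-visit correlation enters, because only one visit is used.

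**Time point.** If the SD is 10.5 at each visit, the effect is the same at each visit and any two visits correlate at ρ (all assumed), the average of four visits has SD 10.5 × √((1 + 3ρ)/4). Pooled power is then 98.2%, 94.2% and 88.7% at ρ = 0.3, 0.5 and 0.7, against 79.7% at Day 28. The two readings are different tests.

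**Model.** With a treatment-by-strata term, the pooled difference is w × d1 + (1 − w) × d2, where d1 and d2 are the treatment differences in two strata. It changes with w whenever d1 and d2 differ, and its precision depends on w in any case. SAP 4.3.1 gives no w. Without that term, as in Protocol 15.3.8 and as the footnote lists the model, the question does not arise. So the specifications need not return the same number.

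**The case against.** The case for leaving the plan alone is that the intent is plain. SAP 3.1, the primary objective and the two-level treatment factor all point to pooled B244 versus placebo. The pooled result is in the Table 14.2.1A shell, and the by-visit p-values are already called nominal. The trial is Phase II. Part of this stands: pooled B244 is the likely intent. But intent is inferred rather than stated, Protocol 15.1 describes the groups differently, and no non-nominal primary test is defined anywhere.

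Some stronger readings are tempting but not supported:

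- *The pooled contrast is missing.* It is planned; what is missing is its designation and its time point.
- *The error rate is that of all 12 systolic p-values* (about 19% to 33% for between-visit correlation 0.9 to 0.3). This needs an assumed correlation, and nothing in the SAP lets any of the 12 be declared the primary success.
- *Each dose is compared with same-spray placebo, 26 versus 26.* SAP 3.2, SAP 3.5 and the shells largely settle the comparator as pooled placebo, and SAP 4.3.1 makes within-strata comparisons exploratory.
- *The per-protocol definition fixes Day 28.* SAP 2.1 requires a Day 28 reading, but Protocol 15.2, the Table 14.1.1 footnote and Listing 16.2.1 accept any post-baseline reading.
- *The footnote is a deliberate second model.* NIS-W suggests carried-over text, and its list of terms is not worded as exhaustive. It still conflicts with SAP 4.3.1 as written.
- *The strata interactions cost a known amount of power.* No document gives the split between strata or a difference in effect between them, so no figure can be attached.

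**Conclusion.** The point holds and should be fixed. It goes beyond missing detail, because the per-dose tests as written do not have the stated power: 62.2% and 75.5% instead of about 80% and 90%. Three unranked Day 28 contrasts, each at 0.05, roughly double the false-positive chance (about 10% two-sided, about 5% favouring B244) if any one could be claimed as success. The SAP does not say that it could, nor does it rule it out.

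The power figures assume equal dropout across the four groups and an unadjusted two-sample t-test, as in SAP 3.1; baseline adjustment may raise all of them. Whether the primary time point is Day 28 or an average over Days 7 to 28 cannot be settled from the documents. If pooled B244 at Day 28 is named, the SAP 3.1 calculation stands unchanged.

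**What to change.** Before unblinding:

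- **SAP 4.3 and 4.3.1:** name one primary test: pooled B244 versus pooled placebo, in-clinic systolic change from the MMRM, ITT population, two-sided 0.05, at Day 28. If the sponsor meant the average over Days 7 to 28, say so explicitly. Label the per-dose contrasts (against pooled placebo) and the other-visit contrasts as non-primary with nominal p-values.
- **Model:** use one MMRM specification in SAP 4.3.1 and the Table 14.2.1A footnote, and correct NIS-W. Either state the stratum weights for the pooled difference or keep the treatment-by-strata terms for the exploratory strata analysis. Either choice is acceptable.
- **SAP 3.1:** say that the 80% and 90% power apply to the pooled comparison only, and give 62.2% and 75.5% for one dose against pooled placebo.
- **SAP 5:** record that the groups of 58 are now B244 and placebo rather than spray cohorts, and any change from the Protocol 15.3.8 model.

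The cost is a few sentences and one footnote, with no extra patients or visits. The downside is that dose-specific and other-visit p-values can no longer carry the primary conclusion. If the strata interactions leave the primary model, differences between strata are seen only in exploratory analyses.

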In addition to the model results, descriptive statistics will be presented by treatment for actual value and change from baseline at each visit (Days 0, 7, 14, 28, and 42). Tabulations will be performed for both the ITT and PP populations. Statistics will also be presented for the subgroups of African-American/non-African-American, pre-hypertension/Stage 1 hypertension, male/female, and age <60/ 60 subjects in the ITT population. Additionally the mean difference between the active treatment group and the placebo for each category of the subgroup along with the 95% confidence interval and p value will also be presented. In addition, mixed model analyses of change from baseline will be performed separately for the pre-hypertensive and Stage 1 subjects using both ITT and PP populations.

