Source: [Listing 16.2.6.1](#)

PROGRAM NAME: XXXXXXXXXXXXXXXXXXXXXXXXXXXXXXXXXXXXXXX

DATE: HH:MM/DDMMYYYY

PROGRAMMING NOTE: Continue for Diastolic Blood Pressure Mixed Model Analysis.

Repeat Table 14.2.1A for:

Table 14.2.1B Summary of Values and Change from Baseline for Systolic and Diastolic Blood Pressure - Mixed Model Analysis (PP Population)

Table 14.2.1C Summary of Values and Change from Baseline for Systolic and Diastolic Blood Pressure by Race - Mixed Model Analysis (ITT Population)

Table 14.2.1D Summary of Values and Change from Baseline for Systolic and Diastolic Blood Pressure by Hypertension Stage - Mixed Model Analysis (ITT Population)

Table 14.2.1E Summary of Values and Change from Baseline for Systolic and Diastolic Blood Pressure by Gender - Mixed Model Analysis (ITT Population)

Table 14.2.1F Summary of Values and Change from Baseline for Systolic and Diastolic Blood Pressure by Age Group - Mixed Model Analysis (ITT Population)

PROGRAMMING NOTE: Replace Visit with each subgroup as applicable per table title. P-values and LSMEANS are not required for any subgroups except hypertension stage.

Table 14.2.2A

Change from Baseline at Day 28 ANCOVA Model for Systolic and Diastolic Blood Pressure (ITT Population)

Parameter: Systolic Blood Pressure

		B244			
Visit	Statistic	4 Sprays (N=xx)	8 Sprays (N=xx)	All B244 (N=xx)	Placebo (N=xx)
Day 28	LS Mean (SE)	xx.x (xx.xx)	xx.x (xx.xx)	xx.x (xx.xx)	xx.x (xx.xx)
	95% CI	xx.x	xx.x	xx.x	xx.x
	LS Mean Difference (SE) (Placebo-Active)	xx.x (xx.xx)	xx.x (xx.xx)	xx.x (xx.xx)	
	95% CI for Mean Difference	Xx, xx	Xx, xx	Xx, xx	
	P-value (vs Placebo)	0.xxxxx	0.xxxxx	0.xxxxx	
	P-value (vs 8 Spray)	0.xxxxx			

LS: Least-squares. SE = Standard Error. CI = Confidence Interval.

Model: The ANCOVA model includes the change from baseline as the dependent variable, treatment and strata as factors and baseline value as a covariate.

Source: [Listing 16.2.6.1](#)

PROGRAM NAME: XXX

DATE: HH:MM/DDMMYYYY

PROGRAMMING NOTE: Continue for Diastolic Blood Pressure.

Repeat for:

Table 14.2.2B Change from Baseline at Day 28 ANCOVA Model for Systolic and Diastolic Blood Pressure (PP Population)

Table 14.2.2C Change from Baseline at Day 28 ANCOVA Model for Systolic and Diastolic Blood Pressure by Hypertension Stage (ITT Population)

Table 14.2.3A

Summary of Values and Change from Baseline for Ambulatory Blood Pressure (ABP Population)

Parameter: Systolic Blood Pressure

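### The B244-minus-placebo differences by race, sex and age have no specified adjustment for baseline blood pressure or strata, and the SAP text and its table shells disagree on whether p-values are shown

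*SAP*

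**What the plan says.** For the whole population, SAP 4.3.1 specifies a mixed model for change from baseline: "The model will include stratification factors of spray number and hypertension and baseline blood pressure as covariates". It asks for adjusted LS means and differences in LS means.

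The paragraph on descriptive statistics then lists subgroups by race, hypertension stage, sex and age, and adds: "Additionally the mean difference between the active treatment group and the placebo for each category of the subgroup along with the 95% confidence interval and" a p-value. The next sentence adds a model for one of these factors only: "mixed model analyses of change from baseline will be performed separately for the pre-hypertensive and Stage 1 subjects".

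In the shells (SAP 7.1.1), Tables 14.2.1C (race), E (sex) and F (age) carry Mixed Model Analysis in their titles. They repeat Table 14.2.1A, whose footnote describes a model with baseline blood pressure and hypertension status. The programming note below them reads: "P-values and LSMEANS are not required for any subgroups except hypertension stage".

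**The concern.** Change in blood pressure depends on baseline blood pressure through regression to the mean. Randomisation is stratified by hypertension status (SAP 1.2.2), not by race, sex or age, so within a category of those factors the arms can differ by chance in baseline pressure beyond the coarse stage split. A raw difference in change scores carries part of that imbalance and has a wider interval than an adjusted one, although every subject's baseline value and strata are already in the database. Blood pressure change by ethnic group is a stated exploratory objective (SAP 1.1.2.3), so these outputs will be read.

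There is also a conflict within the SAP. A programmer following 4.3.1 would produce a p-value by race, sex and age; one following the shell note would not. Neither instruction leads to an LS mean in tables whose titles announce a mixed model.

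**Working it through.** **1. Which estimator is planned?** Three features of the SAP point to a raw difference.
- Where 4.3.1 wants a model estimate it says adjusted LS mean or difference in LS means. Here it says only mean difference, within a descriptive paragraph.
- The separate mixed models by hypertension stage are introduced as an addition. They would be largely redundant if the preceding differences already came from such a model.
- The shell note requires no LS means for race, sex or age, and the subgroup version of the ANCOVA table (14.2.2C) is by hypertension stage only.

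Against this stand the table titles and the Table 14.2.1A footnote. On either reading, no baseline-adjusted treatment difference within a race, sex or age category is specified.

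**2. The plan's own figure.** Inputs from SAP 3.1 and 3.2: "treatment effect = 5.8 (mean change in systolic blood pressure from baseline), standard deviation (SD) = 10.5", "with alpha = 0.05, using a 2-sample t-test", and "all tests conducted at the 2-sided, 0.05 level of significance". With 52 per arm, the noncentral-t power is 79.7% (normal approximation 80.4%), which reproduces the stated 80%. The second scenario, SD 9, gives 90.2% against the stated 90%.

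**3. Effect of adjusting for baseline.** Assumptions not in the documents: the baseline-to-follow-up correlation r, equal variances at baseline and follow-up, and the subgroup size. Half of the 52 completers per arm gives 26 v 26.

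Var(adjusted) / Var(change) = (1 − r²) / [2(1 − r)] = (1 + r)/2, so the adjusted SD is 10.5 × √((1 + r)/2).

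| r | Adjusted SD | Power, 26 v 26 | Gain over raw 49.7% |
|---|---|---|---|
| 0.5 | 9.09 | 61.6% | 12 points |
| 0.6 | 9.39 | 58.9% | 9 points |
| 0.7 | 9.68 | 56.3% | 7 points |
| 0.8 | 9.96 | about 54% | 4 points |

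At 13 v 13, power is 27.2% raw, 34.5% at r = 0.5 and 31.1% at r = 0.7.

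For the 95% CI, t(0.975, 50 df) = 2.009. The raw half-width at 26 v 26 is 2.009 × 10.5 × √(2/26) = 5.8 mmHg. Adjusted, it is 2.009 × 9.09 × √(2/26) = 5.1 at r = 0.5 and 2.009 × 9.96 × √(2/26) = 5.5 at r = 0.8, ignoring the degree of freedom spent on baseline.

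**4. The same loss seen as chance imbalance.** Baseline SD = 10.5/√(2(1 − r)). A baseline imbalance of one standard error moves the raw difference in change by (1 − r) × baseline SD × √(2/n).
- r = 0.5, n = 26: 0.5 × 10.5 × 0.277 = 1.5 mmHg.
- r = 0.8, n = 26: 0.2 × 16.6 × 0.277 = 0.9 mmHg.

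This is not an additional loss, because Var(change) − Var(adjusted) = (1 − r)² × Var(baseline). At r = 0.5 and n = 26: raw SE² = 2.91² = 8.48, adjusted SE² = 2.52² = 6.36, and the difference of 2.12 equals 1.46².

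**The case against.** The strongest reply is that nothing in the SAP calls these differences unadjusted. A reader might infer that raw differences are a stated decision. The documents do not support that: the estimator is left open, and the titles and footnote point towards a model. What stands is that no adjustment is specified and that the raw reading is the natural one.

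If the shell note governs, the race, sex and age outputs carry no p-values, so there is no test whose power could fall. That is fair, and the conflict has to be settled either way. The interval promised in 4.3.1 would still be wider than it needs to be.

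A reader might also infer bias. Under randomisation the raw difference is unbiased on average, and a change score already removes part of any baseline imbalance. The cost is precision, and the imbalance shift is that same cost in other units.

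Nor is it right that race appears in no adjusted analysis. SAP 3.6 plans race, BMI category and smoking as covariates in exploratory analyses, and 4.3.5 allows race into the 4.3.1 models. Those provisions do not by themselves give a treatment difference within each category. Likewise, the raw results are not wholly without a counterpart for hypertension stage, because the same mean difference is planned there too.

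Finally, r and the subgroup sizes are assumed and the SAP claims no subgroup power. Even adjusted, a half-size subgroup stays well short of 80%.

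**Conclusion.** The point holds as a minor improvement and a reconciliation. SAP 4.3.1 leaves the estimator for the race, sex and age differences undefined, reads most naturally as a raw comparison, and contradicts the note under Table 14.2.1 on p-values. If the differences are raw, the cost in a 26 v 26 category is about 4 to 12 power points, or roughly 0.3 to 0.8 mmHg of CI half-width (5.8 against 5.5 to 5.1), for r from 0.8 to 0.5. These sizes rest on the SAP's 5.8 and 10.5, equal variances, and an assumed r and subgroup size. The direction holds for any r below 1, apart from the small cost in degrees of freedom. No figure is offered for the separate contribution of the strata. The main analysis is unaffected.

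**What to change.** In SAP 4.3.1, replace the subgroup mean difference for race, sex and age with the Day 28 LS-mean difference, all B244 v placebo, with 95% CI and nominal p-value in each category. Fit one mixed model per subgroup factor:
- retain from 4.3.1 treatment, visit, treatment*visit, and main effects of baseline blood pressure, hypertension status and spray number;
- add subgroup and treatment-by-subgroup terms, each also by visit, so that the model compares categories as the exploratory objective requires;
- omit the strata interactions in all these subgroup models, so that the covariate set is fixed in advance and does not depend on category size.

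Change the note under Table 14.2.1 so that LS means, differences and p-values appear in Tables 14.2.1C, E and F, which also makes their titles accurate. Label the results exploratory.

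The cost is SAP wording and a little extra programming on a model already being coded, with no new data. The downside is possible instability of the estimates in very small categories.
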